3.2 AIM 2: Participants and Recruitment

For Aim 2, inclusion criteria include: ≥ 18 years of age; currently smoking ≥ 3 cigarettes per day for the past year; functioning telephone number; owns a smartphone capable of supporting AR and willing to download the study app; and can speak, read, and write in English. The smoking criteria were selected to obtain a wide range of smokers who would have developed both sufficient cue reactivity and cessation motivation (Shiffman et al., 2014). Recruitment (N=2072) will take place via Tobacco Free Florida's Quitline. Upon calling the quitline and enrolling in quitline services, participants will be provided with information about the study by quitline enrollment agents to determine initial interest. A brief eligibility screening will be conducted (e.g., confirm English-speaking, smoking status); eligible callers will be asked for their consent for the quitline to send their contact information to the study team. Enrollment agents will send referrals to study staff daily either via a secure email or secure file transfer protocol. Upon referral receipt, study staff will call participants to complete eligibility screening and conduct the full informed consent process. Then, participants will be randomized to one of the two study conditions. A baseline survey will be sent to participants and study staff will textlinks to participants to download the study app after survey completion, provided the participant reports not being currently abstinent for more than 7 days. Participants are considered enrolled in the study following app download. Participants may withdraw at any time for any reason by contacting the staff and informing staff of their desire to withdraw from the study. These procedures have already been developed in conjunction with the Tobacco Free Florida Quitline. We have allotted 29 months for recruitment, which requires consenting an average of 17 participants per week. Figure 5 presents the expected flow of participants. Thus, the recruitment process is feasible with respect to sample size, quitline burden, research staff burden, and funding duration.

[figure not shown]

Figure 5. Participant Flow Through Study

4. STUDY DESIGN AND METHODS

4.1 Design

The proposed study will test the efficacy of the AR app while also assessing key constructs related to optimizing future implementation. Utilizing a hybrid design in partnership with the Florida Tobacco Quitline, we will recruit and randomize participants to one of two treatment arms: (1) quitline only (QLO) or (2) quitline plus the AR app (QL+AR).

4.2 Intervention

Participants in the QL + AR condition will download and use a smoking cue extinction app that includes the features outlined in Table 1.

Table 1. AR App Features

FEATURE	DESCRIPTION	RATIONALE
Situation Menu	Participants will choose what situations/times of day are most appropriate for their AR sessions, although the app will provide general recommendations.	Tailoring treatment content to the individual and supporting choice; ¹ supporting autonomy. ²
Tutorials	Video tutorial on correct app use (e.g., placing AR stimuli), with unlimited interactive practice sessions.	Supporting competence; identified as a needed feature in preliminary work by the investigative team.
Rationale for Cue Exposure	Rationale for cue exposure to help quit smoking/support participant goals (video).	Supporting autonomy; ² providing purpose of the app and improving knowledge of benefits. ¹
Best Practices for AR Sessions	Specific guidelines for using the app (e.g., no smoking during sessions; no use of nicotine products before sessions, patch use ok).	“Expert advice” is an ideal feature for quit smoking apps. ³
Reminder Notifications	Participants will select frequency of reminder notifications to complete AR sessions.	Supporting autonomy; ² participants prefer to choose timing of reminders. ³
Progress Tracker	Participants will be able to view 1) their progress through the program overall, 2) changes in urge ratings over time, 3) daily cigarette use, and 4) use of NRT.	Supporting competence; ² consistent with mHealth frameworks; ¹ preferred feature in quit smoking apps. ^{3,4}

Troubleshooting	Available any time to support use of the app.	Quick access for app support.
Rewards	Linked app engagement and progress towards quitting (e.g., visual presentation of money saved by not smoking).	Rewards for quitting smoking commonly requested feature. ³
App Coach	Link to live App coaching by phone call.	Offers additional explanation of extinction goals as well as technical assistance for app.

¹Floryan et al., 2016; ²Ryan & Deci, 2000; ³Hartzler et al., 2016; ⁴McClure et al., 2016

App Use

Initial use of the app will occur in stages: Assess, Setup, Recommendations for Use, and Extras. Once users complete the stages, they will be able to use the app as needed on a daily basis. We describe all aspects of the app below, including those only relevant to Aim 2.

Assess. Each morning, participants will be prompted to complete a daily diary to assess the following from the previous day: number of cigarettes smoked, NRT use, and tobacco craving. Because ongoing smoking during cue-exposure sessions will be counter-productive to extinction of urges, participants will need to self-report 48 hours of abstinence to advance to Setup. Achieving such short-term abstinence with quitline support/NRT should be feasible for at least 70% of participants (Shiffman et al., 1996; Shiffman et al., 2007).

Setup. Once the abstinence requirement is met, participants will personalize the app, learn the purpose of the app, and practice using AR. First, they will watch a video tutorial explaining the use of cue exposure. They will select their most relevant AR cues and situations in which they most commonly smoke and/or experience high cravings (e.g., upon waking, after meals, when stressed, with alcohol, with coffee, celebrating). They will receive a list of “best practices” for completing AR sessions (e.g., no smoking during sessions). Participants will next receive instruction on using the app for cue-exposure sessions, comprising a short video describing how to place the AR objects, followed by an interactive tutorial with real-time practice.

Recommendations for Use. Recommendations for daily use will be proactively provided, but also available for later review on demand. The app will recommend that participants complete 2-5 AR sessions per day. It will emphasize that the more often they use the app when experiencing craving, the more successful they will likely be in maintaining abstinence.

Extras. Participants will be introduced to all other features of the app: setting up reminder notifications, accessing the progress tracker, access to the App coach, and viewing of rewards.

Details of AR Sessions. Participants will be encouraged and reminded to complete 2-5 AR sessions per day. Each session will present 3-8 cues, and each cue will be presented for 20-40 seconds (average amount of extinction per day will be about 10 minutes). We have included variability in the number and length of cue presentations to decrease predictability and maintain general interest in the sessions. Participants will be encouraged to conduct the AR sessions when high cravings are expected. Before beginning an AR session, participants will indicate their current situation/environment (e.g., after meal), and current urge to smoke and then a series of AR cues will be presented. Participants will rate their urge to smoke following the first and last cue in the session. Data will be automatically uploaded to the cloud.

4.3 Procedure

Aim 1: AR App Updates and Usability Testing

Aim 1 Overview

Aim 1 will include updates/modifications to the AR app, along with participant usability testing to finalize the product for use in Aim 2. In collaboration with Haneke Design, we will develop additional AR smoking-related stimuli, totaling 12 to 20 AR images. Given our previous experience developing smoking and neutral AR stimuli, we believe this process will take relatively little time to complete. We will also update the AR app with additional content for Aim 2 (e.g., menu options) and make the app functional for both Apple and Android devices. We will field-test the revised app with 10 participants, and adjust software and methodology as needed prior to Aim 2. Concurrently, [name] will work with her team at RVO Health to modify the existing software of the Tobacco Free Florida Quitline to facilitate recruitment for Aim 2, and train quitline enrollment agents on caller screening and study referral. Aim 1 will take 12 months to complete (see attached Timeline).

Development of Additional Stimuli and App-based Content

Currently, the AR app is only available on iOS, Apple's operating system, so Aim 1 will update the app to be compatible with both Apple and Android operating systems. We already developed 6 AR smoking cues (Figure 4), and we will create 6-14 additional images. We anticipate a subset of these cues to include motion (e.g., smoke rising) and some combined cues (e.g., lighter, ashtray, and pack of cigarettes). The process for developing these cues will mimic the procedures from our R34 project.

Although the app will function as an adjuvant to quitline phone counseling, we will include specific functionality and features within the app that complement the AR sessions. These features are based on: (1) current recommendations for mHealth interventions, guided by both self-determination theory (SDT) and the behavioral intervention technologies (BIT) model (Floryan et al., 2016; Mohr et al., 2014); (2) recommendations for smoking cessation apps (Hartzler et al., 2016; Heffner et al., 2015; McClure et al., 2016; Ortis et al., 2020); and (3) our experience developing the first iteration of the app. To increase intrinsic motivation and engagement, we utilized SDT as a guiding framework when deciding on features to include, with a primary focus on supporting autonomy and competence (Deci et al., 1994; Ryan & Deci, 2000; Williams et al., 2006). Given modest rates of treatment adherence for existing smoking cessation apps (Abroms et al., 2013), it is important to integrate features that enhance engagement. Social support is often recommended for smoking cessation apps (e.g., Hartzler et al., 2016; Heffner et al., 2015), but because this app will be an adjuvant to quitline counseling, we will not include a comprehensive support feature. That said, we are interested in knowing whether participants require additional support for the AR and cue-exposure components, and we have incorporated the option of utilizing an App coach via two routes.

Table 1 (above) includes primary app features and rationale for inclusion. Consistent with SDT and general recommendations for mHealth apps (e.g., Floryan et al., 2016), we have incorporated participant choice into the features whenever possible. We expand on those features that require additional rationale here. First, "Rationale for Cue Exposure" will provide a foundation for the use of cue exposure to aid in quitting smoking and will offer information on why cue exposure is important for their personal goal to quit. Second, "Best Practices for AR Sessions" will provide guidelines for using the app that are specific to tobacco (e.g., no smoking during cue-exposure sessions; no use of acute-delivery nicotine products before the sessions). Content from "experts" has been identified as a desirable app feature (Hartzler et al., 2016).

Participants (see 3.1 above)

Informed Consent and Assent

All consenting procedures described here apply to both smokers and quitline supervisors. Prior to enrolling in the study, interested participants will speak with study staff at TRIP to learn more about the study. At that time they will be provided with a detailed overview of the study. Potential participants will be screened for inclusion/exclusion criteria. If eligible, the informed consent process will take place, which includes study personnel providing a detailed description of the study, answering questions, and obtaining verbal consent to participate. We will apply for a waiver of written consent from our IRB. If this is not approved, we are prepared to collect electronic consent via REDCap, which our institution has setup to be a secure, HIPAA-compliant way to document consent from participants. Participants will be given as much time as needed to ask questions during the consenting process, prior to agreeing to participate. Assent is not applicable to our study, as all participants must be over the age of 18.

Recruitment and Procedures

All Aim 1 procedures will be conducted remotely. Recruitment will take place on social media and other websites. Interested individuals will either directly call the study phone line or complete online contact forms and be called back, and additional information about the study will be provided. Interested participants will be screened for eligibility and complete the informed consent process. Staff will provide an overview of general issues about which we will seek feedback (e.g., functionality). Participants will be sent a REDCap survey to

Figure 4. Existing AR Smoking Cues

complete when the call is over. When the survey has been completed, participants will then be texted a link to download the app onto their personal device and use the app in their natural environments for 1 week. A second survey will be sent at the end of the week, followed by a phone interview. Participants will be paid \$10 for completing the baseline survey, \$20 for the follow-up survey and \$15 for completing the phone interview.

App Use (see 4.2 above)

Aims 2 and 3: Randomized Controlled Trial

Project Overview

The primary goal of Aim 2 is to test the incremental efficacy of the AR app when added to standard tobacco quitline services. We will recruit and randomize participants to one of two treatment arms: (1) quitline only (QLO) or (2) quitline plus the AR app (QL+AR). In the interest of rapid dissemination and implementation pending positive findings, we have designed procedures with future scalability in mind. Participants will be recruited via the Tobacco Free Florida Quitline and referred to the study team via quitline enrollment agents. Participants who return a baseline questionnaire will be directed to download the app on their personal device and will complete the study. The primary outcome will be biochemically-confirmed tobacco abstinence assessed at around 6 months in a subset of participants.

Participants and Recruitment (see 3.2 above)

Randomization

Block randomization (block sizes=8) will be used to assign 2072 enrolled participants to one of the two conditions. The randomization order will be generated by [name] and implemented within REDCap.

Quitline Services

All study procedures have been developed in close coordination with Tobacco Free Florida, the Florida Department of Health, and RVO Health, the quitline contractor will oversee all aspects of the quitline, including supervising staff to coordinate project activities, modification of quitline software to support the screening and referral of callers, and management of data collection by quitline staff.

The Florida Tobacco Quitline is operated by RVO Health, the largest provider of tobacco cessation quitlines in the U.S. RVO Health's Quit For Life® program is an evidence-based tobacco cessation treatment delivered over phone, web, and text, and is grounded in social cognitive theory and the U.S. Public Health Service clinical guidelines (PHS Guideline, 2008). Quitline coaches use cognitive behavioral therapy, reinforcement, and principles of self-efficacy to promote effective behavior change. The quitline approach includes 5 key elements: setting a quit date, coping with triggers, effectively using medications, tobacco proofing, and social support. Phone counseling for cessation has been evaluated in randomized trials and effectiveness studies (Hollis et al., 2007; Orleans et al., 1991; Stead et al., 2013; Zhu et al., 2002). Individuals who enroll in the quitline's multi-call program receive three phone calls. They are mailed two weeks of NRT after the first phone call, to begin using on their quit date (coinciding with the second call). Participants will be provided with information about the study during their first phone call, and study staff will reach out to enroll participants in the study after receiving their contact information from the Quitline.

Study Arms

Quitline Only (QLO). Participants randomized to the QLO condition will receive an app that administers the daily diary questions for 5 weeks and shows their app and abstinence related progress. They will not receive any treatment via the app. Thus, they will receive usual care via the quitline and complete minimal daily assessments.

Quitline plus AR (QL+AR). Participants randomized to QL+AR will receive the AR app described in Aim 1. Initially, the app will only administer the daily diary questions. Once 48 hours of self-reported tobacco abstinence is achieved, the AR elements of the app will become available (see 4.2). Daily diary questions will continue for 5 weeks. AR extinction trials will occur daily until (1) the participant reports 3 consecutive days of smoking, in which case the AR trials will be suspended until another smoke-free 48 hours are reported, or (2) a

total of 5 weeks have elapsed since the start of app use.

The integration of cue exposure and quitline treatment is important. Quitline coaches encourage removing all smoking paraphernalia prior to the quit date, which will facilitate tobacco-free AR sessions and reduce risk of post-AR relapse. Notably, the use of AR stimuli for exposure sessions is completely consistent with the instructions to avoid in vivo cues to smoke. Other aspects of quitline treatment (setting a quit date, coping with triggers, using NRT, social support) are well-established tobacco treatment components and should facilitate abstinence.

Although the app is designed to be self-contained, it will include access to an App coach who can provide additional instruction and explanation of the extinction goals and process, as well as technical assistance with the app. App coaching can be initiated through two routes: *on demand* and *triggered*. The *on demand* route allows participants to contact an App coach at any time (9am – 6pm, 7 days/week) via a selection within the app. The *triggered route* is activated based on non-engagement with the app within the first 48-hour post-abstinence period. If AR trials have not been initiated within this period, the app will first send reminder notifications. If these do not yield AR usage within 24 hours, the app will send a notification offering the option of immediate or scheduled connection to an App coach (opt-in). If this is declined and AR disuse continues for another 24 hours, the app will send a notification that an App coach will reach out to them that day. This process may be repeated one additional time. App coaching sessions will focus on the following topics: reinforcing the rationale for cue exposure; addressing any issues related to smoking or NRT use before/during/after cue-exposure sessions; guidance on how to be fully immersed in the exposure sessions; and encouragement to maintain connection with the stimuli during exposures (vs use of any avoidance strategies). Technology-related assistance will also be provided as needed, along with any other concerns brought up by the participant. It should be noted that these topics will be available to view in the app itself. We will monitor the frequency, content, and time required of App coaching to guide future implementation. Data may inform improvements to the app and whether App coaches should be retained—perhaps via specialized training of quitline coaches.

End of Treatment and Follow-up

Follow-up questionnaires will be sent to all participants via REDCap around 5 weeks and 6 months after-baseline completion. A subset of participants (40%, approximately 100) who self-report cigarette smoking abstinence at around 6 months will be mailed a saliva collection kit for cotinine-based biochemical confirmation of abstinence. A subset of participants (n=40) from QL+AR will complete a phone interview at the end of treatment, as will a subset of quitline supervisors (n=10) and all App coaches.

Compensation and Retention

For completion of measures at baseline, and around 5 weeks and 6 months after baseline survey completion, participants will receive a \$20 gift card (up to \$60 total). For each week they complete at least 70% of the daily diary questions (5 days), they will receive a \$10 gift card (up to \$50 total). Thus, most participants will be compensated up to \$110. Participants who complete the interview, will be compensated \$20. Participants who return a saliva sample will be compensated \$25.

To aid in retention, the following procedures will take place: collection of full contact information; text reminders and phone calls to follow-up on incomplete surveys; and collection of names and contact information of at least 2 collaterals (i.e., relatives, friends) who can help us reach lost participants.

Treatment Delivery and Fidelity for AR and Quitline Coaching

Although we expect minimal use of App coaches based on the comprehensive app content, we will monitor and assess coaching fidelity. App coaches will be part of the study team. With an eye toward scalability, qualifications will mimic those of quitline coaches (e.g., Bachelor's degree, tobacco abstinent). Training will be manualized and conducted by Drs. [name] and [name], given their experience with exposure-based treatments. Training (8-10 hours) will be a combination of reading, didactics, and role playing. We will develop a measure to assess adherence and competence to be used during the training period. Weekly supervision will occur to ensure App coaching is delivered consistently. Coaches falling below performance

criteria will receive additional training. To monitor treatment adherence, sessions will be recorded and a random sample of 50% will be rated by the investigators using the measure developed during the training period. Fidelity of the screening and referral process will be conducted by [name] team on a weekly basis by reviewing a subset of call recordings of the study offer and screening, and providing regular feedback to enrollment agents.

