Data Management. Baseline, 5-week, and 6-month survey data will be exported from REDCap as .CSV files, which will be read into SAS version 9.4 (SAS Institute, Cary, NC) on a weekly basis during data collection. Data review and primary data analyses will be performed using SAS version 9.4. [name] will oversee the data management, provide the PIs with reports and summaries on a regular basis, and perform the final analyses.

Sample Size and Study Power Analysis. The primary statistical analysis for Aim 2 will use logistic regression to compare abstinence rates at the 6-month assessment between QL+AR and QLO conditions. Preliminary analyses will be used to identify demographics and tobacco history variables that predict either missing surveys or abstinence around 5 weeks and 6 months. These variables will be used in a multiple imputation model to manage missing data. Based on abstinence rates from quitline/telephone counseling (Fiore et al., 2008; Matkin et al., 2019; Pinero et al., 2020), the estimated 7-day point prevalence abstinence rate around 6 months for the QLO condition is 10%. With 1036 randomized to each condition, power was calculated for the 725 participants expected to achieve 48-hours of abstinence in each condition (to activate the AR app). Power $\geq .80$ to detect an abstinence rate of at least 15% (OR = 1.59) in the QL+AR condition using alpha = .05, a 2-sided test, and allowing 5% of variance in abstinence rates to be accounted for by other variables. A comparable analysis using all 2072 randomized participants (the 1450 who do achieve 48-hours of abstinence plus the 622 who do not) will have lower expected abstinence rates. Estimating that 7% of all QLO participants will be abstinent, power $> .80$ to detect an abstinence rate of at least 10.6% for QL+AR (OR = 1.57) using alpha = .05, a 2-sided test, and allowing 5% of variance in abstinence rates to be accounted for by other variables.

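### A single fixed block size of 8 is printed in the protocol with no concealment described, so someone who followed every allocation in order could determine up to 20% of assignments

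*Combined protocol and SAP*

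**What the plan says.** Section 4.3, Randomization, gives one block size: "Block randomization (block sizes=8) will be used to assign 2072 enrolled participants to one of the two conditions". The order is generated by one person "and implemented within REDCap". Nothing is said about stratification factors, varying the block size, concealment or blinding.

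Section 3.2 gives the sequence of events. After a quitline referral, "study staff will call participants to complete eligibility screening and conduct the full informed consent process". Allocation comes only once consent has been given: "Then, participants will be randomized to one of the two study conditions". The baseline survey follows, and then "study staff will textlinks to participants to download the study app after survey completion". The text does not say whether the same people consent participants and send the links.

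Under Study Arms in section 4.3, the quitline-only app carries the diary and a progress display: "They will not receive any treatment via the app". The other arm's app unlocks the augmented-reality sessions. Section 5 confirms equal arms: "With 1036 randomized to each condition, power was calculated for the 725 participants expected to achieve 48-hours of abstinence in each condition".

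**The concern.** In a balanced block of known size, allocations already made constrain those still to come. Once four of the eight have gone to one arm, the rest of the block is fixed. REDCap can hide the list, but it cannot hide past assignments from anyone who learns them, and arms this different are easy to recognise.

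The people who could act on such knowledge are those who decide, before randomisation, whom to call, when to call, and whether a caller meets a criterion that needs judgement, such as willingness to download the app. If those decisions leaned on the expected arm, the groups could differ in motivation to quit. Adjustment for measured baseline variables would not fully remove that difference.

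**Working it through.** **Inputs.** Block size 8 and N = 2072 (section 4.3). Allocation 1:1, so 4 + 4 per block, from 1036 per arm (section 5). Consent rate 17 per week (section 3.2), which is 17/8, or about two blocks a week.

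**The plan's own figure.** 2072/8 = 259 complete blocks, and 259 × 4 = 1036 per arm. This matches section 5 exactly and is consistent with a single list of blocks of 8. The documents give no predictability figure to reproduce.

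**Certain assignments, full observer.** For a block of 2m, the expected number of forced assignments is 2m/(m+1). With m = 4 this is 8/5 = 1.6 per block, or 1.6/8 = 20%. Over the trial, 0.20 × 2072 = 414.4. Enumerating all C(8,4) = 70 possible blocks gives the same answer by position:

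| Position in block | 1–4 | 5 | 6 | 7 | 8 |
|---|---|---|---|---|---|
| Probability that the assignment is forced | 0 | 0.029 | 0.143 | 0.429 | 1.000 |

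The sum is 1.6.

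**Best guess, full observer.** Always guessing the arm that is behind is right [m + (2^(2m)/C(2m,m) − 1)/2]/(2m) of the time. With m = 4 this is [4 + (256/70 − 1)/2]/8 = 5.329/8 = 66.6%, against 50% by chance.

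**Partial visibility (assumption, because the documents are silent).** Suppose the observer knows the position in the block but sees each earlier allocation only with probability q. Certainty requires seeing all four allocations to the exhausted arm, so the share is 0.20 × q⁴.

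| q | Certain share | Of 2072 |
|---|---|---|
| 1 | 20% | 414 |
| 1/2 | 1.25% | 26 |
| 1/3 | 0.25% | 5 |
| 1/4 | 0.08% | 2 |

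**After the fix.** Take blocks of 8, 10, 12 and 14 with equal probability, and an observer who sees every allocation and knows the set of sizes but not the boundaries. Simulation gives about 0.6% certain assignments (0.006 × 2072, about 12). For the best guess, the formula above gives expected correct guesses per block of 5.329, 6.532, 7.716 and 8.887. Their sum is 28.464 over 8 + 10 + 12 + 14 = 44 assignments, which is 64.7%; simulation agrees.

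**The case against.** The case against is substantial, and much of it stands.

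- **The 20% needs an ideal observer.** That person must know the block size and boundaries and see every earlier allocation in order. The documents do not say who sees allocations or how many staff share the calls. At about two blocks a week, the count would have to be kept continuously across all staff. This stands, and it makes 20% a ceiling.
- **Discretion is limited.** Quitline agents pre-screen callers and refer them daily, and most criteria are factual. This narrows the route but does not close it: willingness to download and the timing of calls remain open to judgement.
- **Baseline adjustment.** Section 5 adjusts for baseline variables that differ at p < .10 and for predictors of abstinence. That helps with measured imbalance only.
- **Eight is not a small block.** Blocks of 4 would force 1/3 of assignments. True, but the size is still fixed and published.
- **Varied blocks barely change guessing.** Running totals still return to balance at each block end, so following the arm that is behind remains useful. This also stands: the fix removes certainty and leaves most of the guessing advantage.

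A reader might also infer that selective pursuit of survey completion or app download belongs here, since "Participants are considered enrolled in the study following app download". It does not. Those steps come after randomisation, when the actual arm may be known and no prediction is needed. Any such loss is a separate issue that varied blocks would not touch.

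**Conclusion.** The point holds as a minor weakness in allocation concealment. A fixed block size is published, no safeguard is described, and study staff screen and consent before randomisation into visibly different arms. At most 20% of assignments (about 414 of 2072) could be known in advance. The share is about 1% or less if half or fewer of the earlier allocations are seen.

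The stronger reading, that consenting staff do know one assignment in five, is not supported. The documents do not show that these staff see past allocations or know where blocks begin. Nothing in them indicates that selection bias has occurred. The absence of stratification is inferred from silence, and the open-label character from the differing apps; neither is stated. The 20% rests on 4 + 4 blocks in one sequence and full visibility.

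**What to change.** Generate the remaining REDCap allocation table with block sizes varied at random, for example 8, 10, 12 and 14, starting where a current block of 8 ends. Remove the sizes from the protocol and keep them with the statistician. Add a sentence saying who can see allocations already made and whether those people also screen and consent; if access is already restricted, that sentence answers much of the concern.

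The cost is one new allocation table. If recruitment stops partway through the largest block, the arms can differ by at most 14/2 = 7, which is negligible at 2072. The target sample size and the analysis need no change. The stated benefit should be the removal of near-certain knowledge (from up to 20% to about 0.6%), since best-guess accuracy would still be about 64.7%.
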